**Figure 2. Narrative Intervention Flow Diagram**

**Narrative Intervention group.** The intervention in this study is a co-created narrative whereby patients share their illness narrative with a research team member through an open-ended, audio-recorded interview about their illness. During the interview, patients are prompted to share their narrative through probing questions or statements such as: tell me about your illness; tell me how your illness has affected your emotions, your relationships, and your spirituality. These probing questions have been field tested during my dissertation research and K99 study. As the patient responds, the research team member takes field notes and audio-records the interview.

The audio-recorded interview is then transcribed verbatim, and the research team member will create a one- to two-page meta-narrative. Criteria are that the patient’s narrative is: 1) written in the patient’s first-person voice; 2) nonjudgmental; 3) captures the patient’s voice; 4) accurately reflects the content of the interview; 5) is Instructions – How to complete the COMIRB protocol template (Social) CF-184, Effective 4-26-2010

non-diagnostic (not labeling). The co-created patient narrative is then returned to the patient within 48 hours, and the patient reads his/her written narrative. At that member checking follow-up session, the patient is encouraged to make any desired changes, which facilitates co-creation of the patient's narrative. Once the narrative is approved by the patient, the patient's narrative will be uploaded to the EHR. Once the narrative is uploaded into the EHR, the assigned nurse will be alerted that the patient's narrative is ready to be read. The workflow diagram is depicted in Fig 2.

**Usual care group.** The intervention group will be compared to a usual care group of participants: hospitalized patients who meet the same eligibility criteria as the narrative intervention group. Because there are few interventions in place to increase communication among patients and nurses, the use of a usual care patient group is the most appropriate comparison.

**Randomization.** Randomization to the narrative intervention or usual care will occur at the patient level. The random allocation sequence will be computer generated using random block sizes, an allocation ratio of 1:1, and stratification by illness group. The project statistician will generate the allocation sequence using SAS software and the allocation sequence will be uploaded for study use into REDCap. Upon study completion, baseline characteristics between intervention and control patients will be compared using independent samples t-tests (continuous measures) and chi-square tests (categorical measures). Though balance is assumed, statistical adjustment will be used in outcome analyses in the event of pre-treatment differences between conditions.

**Data collection.** All survey and demographic data will be captured using electronic surveys through REDCap on password-protected iPads/laptops.

**Demographics.** At baseline, age, gender, race/ethnicity, education in years, income level, religion/spirituality preference, and clinical details to identify co-morbidities and severity of illness will be collected for all participating patients. This demographic detail will allow description of outcome means and standard deviations in key patient subgroups, including groups defined by patient race/ethnicity and specific chronic illnesses of heart disease or end-stage renal disease.

**Measures.** For Aim 1, the primary and secondary outcome measures will be collected at three time points from all patient participants. (Table 1). The purpose of these times periods are to collect the outcome measures consistently for usual care and intervention participants. This is based on knowledge gained during the K99 study regarding time to complete the narrative intervention. In the K99 study, for the narrative intervention, on average it took 24 hours post narrative interview to upload the patient's narrative into the EHR.

**Exit Interviews and Usability Scale.** For Aim 2, the patient and nurse exit interviews and system usability surveys from the nurses will be collected approximately 1-week post intervention. (Table 1).

**Sample Size and Power Analysis.** Sample size estimates were generated to determine power to detect a time by treatment interaction within the proposed repeated measures design. Assuming two-sided alpha = 0.05, a sample size of 80 patients will provide 80% power to detect an effect size associated with treatment effects on changes over time as small as  $f=.14$  (Cohen's  $d = 0.28$ ). This represents a small, clinically relevant effect, but more importantly will provide stable measures of outcome means and standard deviations over time for use in the planned R01 efficacy trial. Modern missing data techniques will be used if patients drop out before all follow-up data is obtained. To minimize concerns for attrition, the time between baseline and follow-up data collection is small. Nonetheless, if patients are lost to follow-up, even if a high level of attrition (e.g., 20%) will allow for the detection of a small effect size of  $f=.16$ .

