## F. Data Analysis Plan.

**Aim 1 Analysis Plan.** Statistical analyses will be performed with the use of SAS software, version 9.4. In preliminary analyses, data will be screened for errors and outliers; appropriate transformations will be made for non-normal outcomes. Baseline demographics will be summarized using standard descriptive statistics. The pattern of participant dropout will be examined to ensure a reasonable equal distribution of participants lost to follow-up between groups and based on baseline characteristics. Maximum likelihood techniques will include participants with incomplete data without need for imputation. In addition, we will conduct sensitivity analyses to examine the effect of departures from key assumptions made in the main analysis and to help determine effects of missing data. Using an intent-to-treat approach, primary and secondary outcomes will be analyzed with linear mixed models using SAS Proc Mixed to compare the two groups (narrative intervention versus usual care) over the assessment period. Separate models will be estimated for each of the primary and secondary outcomes, though relationships among outcomes will also be assessed. Mixed models will specify intervention group and time as fixed effects and subject as a random effect. Pairwise comparisons testing group effects at each time point are proposed to disentangle the effects of intervention process versus change in quality of communication between patient and nurse. All statistical analyses will be done in consultation with the project statistician, [name].

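### Covariate adjustment hangs on baseline tests run at study end, while the illness stratum and the baseline score are left out of the time-point comparisons

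*Combined protocol and SAP*

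**What the plan says.** Section IV.C, Randomization, allocates patients by computer with random block sizes, "an allocation ratio of 1:1, and stratification by illness group". It then has the arms compared at baseline after the study is complete, with t-tests for continuous and chi-square tests for categorical characteristics. The next sentence states that balance is assumed but that "statistical adjustment will be used in outcome analyses in the event of pre-treatment differences between conditions". No significance level, covariate list or other criterion is given.

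Under Measures in the same section, "the primary and secondary outcome measures will be collected at three time points from all patient participants", and Table 1 shows baseline as the first of the three. The power section is based on "power to detect a time by treatment interaction within the proposed repeated measures design".

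Section F, Aim 1, describes the outcome model: "Mixed models will specify intervention group and time as fixed effects and subject as a random effect". It adds: "Pairwise comparisons testing group effects at each time point are proposed to disentangle the effects of intervention process versus change in quality of communication". The illness stratum, a baseline covariate and a constraint of equal baseline means appear nowhere. The sensitivity analyses promised there concern model assumptions and missing data, not covariates.

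**The concern.** There are three linked problems.

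- **The trigger.** Under correct randomisation every baseline difference is chance. A p-value for such a difference carries no information on whether the variable predicts the outcome, which is what makes adjustment worthwhile. Any covariates added to the core model stay unknown until the data are in, and two analysts could apply the rule differently.
- **The stratum.** Allocation is balanced within illness group, but the model ignores illness group. Variation between the strata then stays in the residual, and standard errors for between-patient comparisons are overstated.
- **The baseline score.** It enters at most as an unconstrained first response. It informs the interaction through change over time, but not the separate group comparisons at Times 2 and 3.

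The plan relies on those separate comparisons to tell the effect of taking part in the narrative process from a change in nurse communication. It also wants an effect size for the later efficacy trial (section IV.C, Design). Both call for the most precise contrast the data can give, with a covariate set fixed beforehand.

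**Working it through.** **Inputs from the documents.** 80 patients, 40 per arm (section D); two-sided alpha 0.05, 80% power, f = 0.14, or f = 0.16 with 20% attrition (Sample Size and Power Analysis); three assessments (Table 1); eight baseline items listed under Demographics: age, gender, race/ethnicity, education, income, religion/spirituality, co-morbidities, severity.

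**Assumptions.** The documents give no correlation between baseline and follow-up (0.3, 0.5 and 0.7 are used), no test threshold (0.01, 0.05 and 0.10 are used) and no size for the illness-group effect (5%, 10% and 20% of variance are used). Co-morbidity and severity are counted as one variable each.

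**1. The plan's own figure.** For the interaction with m = 3 times and 2 groups, λ = f²·N·m/(1−ρ), with df 2 and 2(N−2).
- N = 80, ρ = 0.5: λ = 0.0196 × 80 × 3 / 0.5 = 9.41, power 78.2%; f for 80% power is 0.143.
- N = 64: λ = 0.0256 × 64 × 3 / 0.5 = 9.83, power 79.8%; f for 80% power is 0.160.

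Both stated values reproduce, and nothing below disturbs them.

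**2. How often the trigger fires by chance.** With k independent tests at level a, the probability is 1 − (1−a)^k. For k = 8:
- a = 0.05: 1 − 0.95⁸ = 34%
- a = 0.01: 8%
- a = 0.10: 57%

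If the 11 baseline outcome scores (QOC, eight PROMIS-29 domains, two illness-impact scores) were tested too, k = 19 and the figure at 0.05 is 62%. Any one score, including the baseline QOC, would be picked only about 5% of the time.

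**3. What the time-point comparison uses.** A mixed model with group-by-time terms and a random subject effect was fitted to simulated complete data. The Time 3 group contrast equalled the raw difference in means (largest discrepancy 4 × 10⁻¹⁵). Constraining the baseline means to be equal cut its variance to 0.76 of that value at ρ = 0.5.

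**4. Precision lost.** In SD units, SE = √(4/80 × (1−ρ²)), with ρ = 0 for the unadjusted comparison. The half-width is t(0.975) × SE, and the detectable difference comes from the noncentral t.

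| | Unadjusted | ρ = 0.3 | ρ = 0.5 | ρ = 0.7 |
|---|---|---|---|---|
| SE | 0.224 | 0.213 | 0.194 | 0.160 |
| Variance reduction | – | 9% | 25% | 49% |
| 95% CI half-width | 0.445 | 0.425 | 0.386 | 0.318 |
| Detectable, 80% power | 0.634 | 0.605 | 0.549 | 0.453 |
| Power at 0.28 SD | 24% | 25% | 30% | 41% |

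At ρ = 0.5 an unadjusted comparison would need 40/(1−0.25) ≈ 53 patients per arm to match 40 adjusted.

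**5. The rule in action.** Simulation, 40,000 trials per setting, 40 per arm, normal data, rule applied to the baseline outcome score at 0.05. The illustrative difference reads f = 0.14 as a full, equal effect at Times 2 and 3: 0.14 × √18 = 0.594 SD.

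| | ρ = 0.3 | ρ = 0.5 | ρ = 0.7 |
|---|---|---|---|
| Power, test-then-adjust | 75% | 76% | 76% |
| Power, always adjusted | 78% | 85% | 95% |
| Power, change from baseline at Time 3 | 60% | 75% | 92% |
| Unadjusted and adjusted on opposite sides of 0.05 | 8% | 14% | 22% |
| Type I error, test-then-adjust | 4.8% | 4.2% | 3.7% |

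The change-from-baseline row is a stand-in for the interaction. The three-time interaction itself, from the formula in step 1 at f = 0.14, has power 63%, 78% and 95%.

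**6. Omitted stratum.** If illness group explains R² of the variance, intervals are too wide by 1/√(1−R²) − 1 and the true alpha is 2(1 − Φ(1.96/√(1−R²))). For R² = 0.05, 0.10 and 0.20 the excess width is 3%, 5% and 12%, and alpha is 4.4%, 3.9% and 2.8%. A stratum effect that is constant over time cancels from the interaction.

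**The case against.** The strongest reply is that little is at risk. This is a proof-of-concept study, the sample size is powered on the interaction, the interaction already uses baseline, and the rule does not inflate type I error. All of that is correct, and it limits the point to precision and pre-specification.

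Other objections stand in part:
- That the tests trigger adjustment is read from two adjacent sentences. It is the natural reading, and no other criterion is offered.
- The statement that the time-point comparisons ignore baseline is exact only with complete data. With missing follow-up, the likelihood analysis borrows a little from it.
- The power section's remark that the sample size "more importantly will provide stable measures of outcome means and standard deviations over time" is weak support. Raw means and SDs do not depend on the covariates; the gain is in the treatment contrast.
- At the plan's own d = 0.28 the time-point comparisons have low power with or without adjustment (24% against 25% to 41%).
- The 34% concerns demographic and clinical variables, while the simulation applies the rule to the baseline outcome score alone. Each illustrates one part of the rule; neither represents the whole.
- No figure in the documents supports the range used for the stratum effect.

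None of these supplies a reason to keep the trigger, or to leave out a stratum and a baseline score that are already recorded.

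**Conclusion.** The concern holds. As written, additions to the model depend on chance imbalance, the allocation stratum is missing from the model, and the Time 2 and Time 3 comparisons discard baseline information when data are complete. The cost to those comparisons is 9% to 49% of their variance for a baseline correlation between 0.3 and 0.7, modest at the low end and substantial at the high end. Test-then-adjust recovers almost none of it. Leaving the choice open also matters for the reported result: at the illustrative 0.594 SD, the adjusted and unadjusted analyses disagree about significance in 8% to 22% of trials.

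No bias or inflation of overall type I error is claimed, and the stated f = 0.14 and f = 0.16 are unaffected. The correlation, test threshold, stratum effect and illustrative difference are all assumptions. The plan should be changed on this point, but the trial is not invalid without the change.

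**What to change.** - Delete the test-triggered rule. Report baseline characteristics by arm descriptively, without p-values.
- Include illness stratum, as randomised, in every outcome model.
- Choose one way of using baseline and state it:
  1. all three assessments as responses, with a common baseline mean across arms, which keeps the time-by-treatment interaction as the treatment test; or
  2. the baseline value of the same outcome as a covariate, with only Times 2 and 3 as responses, where the treatment test is the joint group effect at those two times.

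  The two should not be combined.
- Name any further covariates before outcome data are analysed. Label any adjustment for observed imbalance as a sensitivity analysis.

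The cost is a few sentences in sections IV.C and F and one or two degrees of freedom. The data are already to be collected, and the randomisation procedure does not change.

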## C. Study Design and Research Methods.

**Design.** This study will use a mixed methods design. The quantitative data will include the patient-reported outcomes on effects of the narrative intervention and will inform potential effect size for the later efficacy trial. The qualitative data will include: 1) patient and nurse exit interviews for triangulation of the quantitative findings and 2) patient’s illness narratives. At this phase of biobehavioral interventional development, both the quantitative and qualitative data give necessary information about acceptability, feasibility, usability for optimization of the narrative intervention.

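### Each outcome's baseline score is adjusted for, if at all, only when the arms are seen to differ, so the follow-up comparisons lose precision that the collected data could supply

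*Combined protocol and SAP*

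**What the plan says.** Under Randomization (Section IV.C), once the study is complete, "baseline characteristics between intervention and control patients will be compared using independent samples t-tests", with chi-square tests for categorical measures. Adjustment depends on the result: "statistical adjustment will be used in outcome analyses in the event of pre-treatment differences between conditions". No threshold is given, no covariates are listed, and it is not said whether baseline Quality of Communication (QOC) is among the characteristics compared. Allocation uses "an allocation ratio of 1:1, and stratification by illness group".

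The Aim 1 Analysis Plan (Section IV.F) states: "Mixed models will specify intervention group and time as fixed effects and subject as a random effect". It adds: "Pairwise comparisons testing group effects at each time point are proposed to disentangle the effects of intervention process". It names no baseline covariate, no common baseline mean and no group-by-time term. Table 1 has QOC and the PROMIS scores collected from every patient at Time 1.

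In the power paragraph of Section IV.C, "Sample size estimates were generated to determine power to detect a time by treatment interaction within the proposed repeated measures design", and the sample "more importantly will provide stable measures of outcome means and standard deviations over time for use in the planned R01 efficacy trial". Under Design, the patient-reported data "will inform potential effect size for the later efficacy trial".

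**The concern.** The text implies, without saying so, that baseline enters the model as a first response with its own mean in each arm. On that reading, with complete data, the group difference at Time 2 or Time 3 equals the difference in raw means at that visit, and the baseline score contributes nothing to it. The interaction does use baseline, but only by subtraction, which is less efficient than regression adjustment at any correlation below 1.

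The conditional rule does not close the gap. Under randomization a baseline difference at p<.05 appears in about 5% of trials, so the adjustment would rarely be used. The rule is also applied after the study ends, with no threshold, which leaves room for discretion.

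What is at stake is the width of the interval around the effect estimate that is meant to inform the efficacy trial. Bias is not at issue.

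**Working it through.** **Inputs.** From the protocol: 40 patients per arm, two-sided alpha 0.05, 80% power, f = .14 at N = 80, f = .16 after 20% attrition (N = 64), three assessments. Assumed: outcome SD 1, equal correlation ρ between visits, complete data, baseline as an unconstrained response. The documents do not give ρ, so .3, .5 and .7 are shown.

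**1. The protocol's own figure.** For the interaction F test, λ = f²·N·3/(1−ρ), with 2 and 2(N−2) degrees of freedom.
- N = 80, f = .14, ρ = .5: λ = .0196 × 240/.5 = 9.41; power 78.2%. The f for exactly 80% is .143.
- N = 64, f = .16, ρ = .5: power 79.8%. The f for 80% is .160.

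So ρ near .5 reproduces both figures. Rounding allows .49–.53, or .58–.62 if only two visits were assumed.

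**2. Precision of one follow-up comparison.** The variance per patient is 1 unadjusted and 1−ρ² with baseline as a covariate. Equivalent n per arm = 40/(1−ρ²). Half-width = t·√(2·variance/n).

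| | ρ = .3 | ρ = .5 | ρ = .7 |
|---|---|---|---|
| Variance cut | 9% | 25% | 49% |
| Equivalent unadjusted n per arm | 44 | 53 | 78 |
| Half-width, unadjusted (SD) | 0.445 | 0.445 | 0.445 |
| Half-width, adjusted (SD) | 0.425 | 0.386 | 0.318 |

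As a check, the standard error from the three-visit model with unconstrained means is 0.2236 SD at every ρ, the same as ignoring baseline. With equal baseline means imposed it is 0.2133, 0.1936 and 0.1597 SD. At ρ = .5, 64 adjusted patients give a half-width of 0.433 SD, narrower than the 0.445 SD from 80 unadjusted patients.

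**3. The conditional rule.** If the trigger is a baseline difference in the same outcome at level a, with two-sided normal critical value z, the share of the variance cut recovered is 1 − [(1−a) − 2zφ(z)].
- a = .05: 1 − [.95 − 2(1.960)(.0584)] = 28%.
- a = .20: 1 − [.80 − 2(1.282)(.1755)] = 65%.

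The reported standard error moves far less. In 20,000 simulated trials it fell on average by 0/0.5/1.3% (p<.05) and 0.5/2/5% (p<.20) at ρ = .3/.5/.7, against 4/13/28% when always adjusted. In a separate simulation of 100,000 trials (ρ = .5, true difference 0.5 SD, p<.05 trigger), power was 60.4% with the rule and 71.6% when always adjusted. Type I error under the rule was 4.2%.

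**4. Power.** For an effect at both follow-ups or at Time 3 only, f = d/√18, so f = .14 corresponds to d = .14 × √18 = 0.594 SD. Results are also given for 0.28 SD, the d stated in the protocol. The joint test after adjustment uses the covariance of Times 2 and 3 conditional on baseline, with 2 and 76 degrees of freedom.

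| Power, ρ = .3/.5/.7 | 0.594 SD | 0.28 SD |
|---|---|---|
| Interaction test, baseline unconstrained | 63/78/95% | 18/23/36% |
| Joint test, adjusted, effect at both times | 89/92/98% | 29/32/43% |
| Joint test, adjusted, effect at Time 3 only | 71/82/96% | 20/25/38% |
| Time 3 comparison, unadjusted | 75% at each ρ | 24% at each ρ |
| Time 3 comparison, adjusted | 79/86/96% | 25/30/41% |

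**The case against.** The strongest reply is that the powered analysis is the time-by-treatment interaction, which uses baseline in every case. Against that test the gain can be small: 78% to 82% at ρ = .5 and 95% to 96% at ρ = .7 when the effect appears only at Time 3. That pattern is plausible for QOC, because the nurse is alerted only after upload and Section IV.D puts the second assessment straight after it. This stands, and the largest gains in the tables should not be read as gains for the interaction test. It does not remove the loss in the per-visit comparisons, which the plan itself proposes, or the larger gain when the effect is present at both follow-ups.

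It is also fair that the sample size section speaks of stable means and standard deviations, and adjustment does not improve the estimate of a raw SD. The argument therefore rests on the Design statement about effect size.

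Other points are right but limit the size rather than the direction. The correlation is inferred from rounded planning figures. The trigger is assumed. With dropout, maximum likelihood lets baseline inform follow-up means to some degree. At 0.28 SD the study is underpowered with or without adjustment. Finally, this is a proof-of-concept study and the planned tests are valid, so the change improves efficiency and does not correct an invalid analysis.

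**Conclusion.** The concern holds and should be fixed. Nothing in the plan commits to using an outcome's baseline score in the follow-up comparisons, and the conditional rule recovers little of what it could give. Per visit, the variance forgone is 9% at ρ = .3, 25% at ρ = .5 and 49% at ρ = .7. For the interaction test at f = .14 and ρ = .5, power forgone is 4 to 14 percentage points, depending on when the effect appears. These sizes assume equal correlation between visits, complete data and an unconstrained baseline mean in each arm. At ρ = .3 the gain at a single visit is modest.

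The unwritten group-by-time term and the absence of a named primary contrast are gaps in wording. They are not evidence that the wrong model would be fitted.

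**What to change.** 1. For each outcome's own baseline value, replace the conditional rule with adjustment in every case. Either use it as a covariate with Times 2 and 3 as responses, or keep all three times as responses and constrain the arms' baseline means to be equal. The provision for other baseline characteristics can stay.
2. Include illness group, the stratification factor, in the model.
3. Drop the between-group outcome test at baseline.
4. Write in the group-by-time term and name one post-baseline contrast, or the joint test, as primary, with the rest supportive.
5. Before choosing a contrast that uses Time 3, reconcile the assessment schedule. Section IV.D gives usual care patients only baseline and one later assessment under the usual care group's data collection activities, while Table 1, Measures (Section IV.C) and Quantitative Data (Section IV.D) give all patients three. Time 2 also differs: Section IV.D places it straight after upload, and Table 1 places it 24–48 hours after baseline or upload. Item 1 holds under either schedule, because with equal correlations the variance cut is the same at Times 2 and 3.

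The cost is a few lines of analysis plan and Proc Mixed code and about two degrees of freedom, with no new data and no change to N = 80. The constrained-baseline form also keeps patients who have only a baseline score, in line with the planned maximum likelihood approach.

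### The sample-size paragraph mislabels its detectable interaction of f = .14 as Cohen's d = 0.28; it is a between-group difference in change of about 0.6 SD, and power at 0.28 SD is about 23%

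*Combined protocol and SAP*

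**What the plan says.** The Sample Size and Power Analysis paragraph in section IV.C opens by naming the tested effect: "Sample size estimates were generated to determine power to detect a time by treatment interaction within the proposed repeated measures design". It sets the error rate ("Assuming two-sided alpha = 0.05") and then states that "a sample size of 80 patients will provide 80% power to detect an effect size associated with treatment effects on changes over time"; it puts the smallest such effect at f = .14, with Cohen's d = 0.28 in parentheses. It comments: "This represents a small, clinically relevant effect". For dropout it adds that "even if a high level of attrition (e.g., 20%) will allow for the detection of a small effect size of" f = .16.

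The paragraph does not give the within-patient correlation, a sphericity assumption, the number of assessments used in the calculation, or the pattern of effect over time. Elsewhere in section IV.C, the Randomization and Measures paragraphs give 1:1 allocation and three assessments for every patient. Section IV.D gives 40 patients per arm.

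**The concern.** The value 0.28 is exactly 2 × .14. The rule d = 2f belongs to a comparison of two independent group means at one occasion. The plan powers something else, a two-group by three-time interaction, where f measures how much the group difference varies across the assessments. A reader who sees d = 0.28 beside a treatment effect on change will take it as a 0.28 SD difference in change between the arms, which f = .14 does not represent.

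At stake is what the trial is said to be able to see on its primary outcome, Quality of Communication. If the detectable effect is about twice the stated one, a null result could be taken to exclude a small effect that the trial had little chance of finding. The same figure could be carried into planning of the efficacy trial.

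**Working it through.** **Inputs.** From the sample-size paragraph: N = 80, 80% power, two-sided alpha .05, f = .14, d = 0.28, and f = .16 with 20% attrition (80 × 0.8 = 64 patients). From the rest of section IV.C: k = 2 equal groups and m = 3 assessments. Assumed, because not stated: within-patient correlation rho = .5 and sphericity. These values reproduce both stated f figures; other values of rho are shown in step 3.

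**Step 1: reproduce the plan's f.** Noncentral F test for the interaction, with lambda = f² × N × m / (1 − rho), df1 = (k − 1)(m − 1) and df2 = (N − k)(m − 1).

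- N = 80, f = .14: lambda = .0196 × 80 × 3 / .5 = 9.41 on 2 and 156 df. Power is 78.2%; 80% is reached at f = .143.
- N = 64, f = .16: lambda = .0256 × 64 × 3 / .5 = 9.83 on 2 and 124 df. Power is 79.8%; 80% is reached at f = .160.

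Both figures match an interaction test. A test of the between-group main effect does not match: at rho = .5 it has 33% power at f = .14, and its detectable f runs from 0.18 to 0.26 for rho from 0 to .5.

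**Step 2: convert f to a difference in change.** Let delta_t be the group difference at time t in outcome SDs. With two equal groups, the interaction deviations in the cells are ±(delta_t − average delta)/2. Hence f is half the root mean square deviation of delta_t from its average over time, and rho does not enter.

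- Equal at baseline, D at both follow-ups (0, D, D): the mean squared deviation is (4/9 + 1/9 + 1/9)D²/3 = 2D²/9, so f = D/√18 and D = .14 × 4.243 = **0.59 SD**. An effect at only one follow-up gives the same value.
- Linear growth (0, D/2, D): the mean squared deviation is D²/6, so f = D/√24 and D = .14 × 4.899 = **0.69 SD**.
- Two assessments only (0, D): f = D/4 and D = **0.56 SD**.

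For a given range over three times, the mean squared deviation is largest when the middle value sits at one end. So 0.59 SD is the smallest range of group differences compatible with f = .14.

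At the exact 80%-power values under the first pattern, the detectable difference is .143 × √18 = 0.61 SD for 80 patients and .160 × √18 = 0.68 SD for 64.

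**Step 3: power if the true difference in change is 0.28 SD (N = 80).** For the first pattern, f = 0.28/√18 = .066 and, at rho = .5, lambda = (0.0784/18) × 480 = 2.09. Power is 23.0%, and a 20,000-run simulation gave 23.3%. For linear growth, f = .057 and power is 18.2%.

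| rho (first pattern) | 0 | .3 | .5 | .7 | .8 |
|---|---|---|---|---|---|
| power at 0.28 SD | 13.5% | 17.5% | 23% | 36% | 51% |

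Power reaches 80% only at rho of about .89, and the detectable f would then be .066, which contradicts the plan's own .14. At rho = .5, 80% power for 0.28 SD needs about 372 patients.

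**Cross-checks.** Two assessments with rho = .6 also come close to the stated figures (f = .142 and .159); power at 0.28 SD is then 28%. A two-sample t test at a single time point with 40 per arm has about 24% power at d = 0.28 and detects 0.63 SD with 80% power.

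**The case against.** The best defence is that the error sits in a parenthesis. The f values reproduce, and section IV.B justifies 80 patients by pilot and usability conventions. The power paragraph itself puts more weight on stable means and SDs for the next trial. No go/no-go rule depends on significance, and the efficacy trial is to be planned from observed estimates. This is a fair account of how far the consequences reach, and it is why the sample size need not change. It does not make the stated d correct.

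Second, the 23% rests on an unstated correlation, sphericity, an effect pattern and the 2-df test. That is true, so it should be read with its range. The 0.56 to 0.69 SD conversion is free of the correlation.

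Third, a sharper analysis would do better. At rho = .5, a 1-df contrast of the mean of both follow-ups against baseline detects 0.55 SD, or 0.45 SD with baseline adjustment; at rho = .7 these become 0.43 and 0.38 SD. But the power paragraph is about the interaction. Section IV.F plans mixed models with pairwise comparisons at each time point, and baseline adjustment is foreseen only if the arms differ at baseline. None of these alternatives reaches 0.28 SD either.

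Fourth, 2f = 0.28 does have a meaning: the root mean square deviation over time of the group difference from its own average. That is not a difference in change, and the paragraph does not present it that way. Finally, the documents give no SD or minimal important difference for the outcome, so clinical relevance is unsupported rather than disproved.

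**Conclusion.** The concern holds. The stated d = 0.28 is wrong as a treatment effect on change, and the description of the effect as small rests on it. The detectable difference in change is about 0.6 SD, roughly twice the stated figure: 0.56 to 0.69 SD at f = .14, depending on the effect pattern and on whether two or three assessments are assumed. This conclusion does not depend on the correlation.

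Power for a true 0.28 SD difference in change is about 23%, assuming three assessments, a correlation of .5, sphericity and an effect present at both follow-ups. It is 18% to 28% across the variants that reproduce the plan's f values, and 18% to 51% for correlations from .3 to .8 under the first pattern.

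**What to change.** In the Sample Size and Power Analysis paragraph, delete the Cohen's d value and the sentence describing the effect as small and clinically relevant, and remove the word small from the attrition sentence. Replacement text could read: with 80 patients the study has 80% power for a group-by-time interaction of f = .14, equivalent to a between-group difference in change from baseline of about 0.6 SD (about 0.7 SD with 20% attrition), a medium-to-large effect; this assumes three assessments, a within-patient correlation of .5, sphericity, and an effect present at both follow-ups.

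The sponsor should confirm the correlation, number of assessments and effect pattern actually used. The .5 is inferred from the reported f values and should be replaced if the original calculation used something else.

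The cost is the wording of one paragraph and a less favourable stated sensitivity. The sample size stays at 80, and neither the design nor the analysis changes.
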